### **Secondary Effectiveness Endpoints**

Due to multiple endpoints, a closed-form hierarchical approach will be used.

Secondary endpoints will be tested in order as follows:

---

 Rom D and B. Holland. (1995). A new closed multiple testing procedure for hierarchical families of hypotheses. Journal of Statistical Planning and Inference 46:265-275

 Rom D, R. Costello, and L. Connell. (1994). On closed test procedures for dose-response analysis. Statistics in Medicine 13:1583-1596

 Marcus R, E. Peritz, and K. Gabriel. (1976). On closed testing procedures with special reference to ordered analysis of variance. Biometrika 63:655-660.

 Huque M and A Sankoh. (1997). A reviewer's perspective on multiple endpoint issues in clinical trials. Journal of Pharmaceutical Sciences 7:545-564.

MONOCULAR DISTANCE-CORRECTED NEAR VISUAL ACUITY (DCNVA) AT 40 CM

The first secondary effectiveness endpoint is mean (LogMAR), monocular DCNVA under photopic conditions at 40 cm at 6 months. Comparisons between lens groups will be performed using a one-sided, t-test with an alpha level of 0.025. Note that a lower LogMAR value is a better acuity and a higher LogMAR value is a poorer acuity. The null hypothesis is that the mean monocular DCNVA LogMAR value for the Model ZHR00 eyes is worse than or equal to that for control eyes. The alternate hypothesis is that the mean monocular DCNVA LogMAR value for Model ZHR00 is better than that for control eyes.

$H_0: \mu_c - \mu_t \leq 0$  (ZHR00 is worse than (higher LogMAR) or equal to control)

$H_1: \mu_c - \mu_t > 0$  (ZHR00 is better (lower LogMAR) than control)

where

$\mu_t$  = the mean LogMAR DCNVA for Model ZHR00 lens

$\mu_c$  = the mean LogMAR DCNVA for control lens

Reject the null hypothesis if one-sided p-value  $\leq 0.025$ .

The success criterion is a statistically significantly lower mean LogMAR DCNVA for ZHR00 compared to ZCB00 ( $p \leq 0.025$ ). In addition, clinical significance will be determined by the median DCNVA of ZHR00 being at least 0.3 LogMAR.

OVERALL SPECTACLE INDEPENDENCE VIA BINOCULAR QUESTIONNAIRE

The second secondary effectiveness endpoint is overall spectacle independence via binocular questionnaire responses and is defined as the subject reporting “No” need for correction for all three conditions (distance, intermediate and near), “None of the time” for correction wear and “None of the time” for strain to see for all four conditions (distance, intermediate, near and overall). Spectacle independence results will be reported by lens group and analyzed by Fisher’s exact test with a one-sided alpha of 0.025. The null hypothesis is that the proportion of Model ZHR00 subjects who are spectacle independent is less than or equal to the proportion of control subjects. The alternative hypothesis is that the proportion of Model ZHR00 subjects who are spectacle independent is greater than that for control subjects.

$H_0: p_t - p_c \leq 0$

$H_1: p_t - p_c > 0$

where

$p_t$  = Proportion of Model ZHR00 subjects who are spectacle independent

$p_c$  = Proportion of Model ZCB00 subjects who are spectacle independent

Reject the null hypothesis if one-sided p-value  $\leq 0.025$ .

The success criterion is a statistically significantly greater proportion of Model ZHR00 subjects who are spectacle independent compared to control Model ZCB00 subjects ( $p \leq 0.025$ ). In addition, clinical significance will be determined as follows:

- The proportion of Model ZHR00 subjects who are spectacle independent will be at least 25 percentage points higher than that for the control group

### **Safety Endpoints**

#### MONOCULAR BEST-CORRECTED DISTANCE VISUAL ACUITY (BCDVA)

The first safety endpoint is mean (LogMAR) first-eye, monocular, best-corrected distance visual acuity (BCDVA) at 6-months postoperative. Results will be compared between lens groups for first eyes using a non-inferiority approach. The null hypothesis is that the mean difference (ZCB00 minus ZHR00) between the test and control IOLs is less than or equal to -0.1 LogMAR, with the alternative hypothesis being that the mean difference is greater than -0.1 LogMAR. A two-sided, 90% confidence interval (CI) will be used for evaluation.

$$H_0: \mu_c - \mu_t \leq -0.10$$

$$H_1: \mu_c - \mu_t > -0.10$$

where

$\mu_t$  = mean LogMAR BCDVA for ZHR00

$\mu_c$  = mean LogMAR BCDVA for ZCB00

The success criterion is that the lower 2-sided 90% confidence interval for the difference between the IOLs is greater than -0.1 LogMAR.

#### RATES OF ADVERSE EVENTS VS. ISO SPE RATES

Rates of adverse events as determined by ISO 11979-1 will be reported through 6 months. The frequency and proportion of first eyes and second eyes with these events will be reported over time by IOL group. Statistical comparisons to ISO SPE rates will be based on first-eye data; adverse event rates for the Model ZHR00 first eyes will be compared to the ISO SPE rates using a one-sided, exact test based on the binomial distribution. The null hypothesis is that the AE rate for the Model ZHR00 eyes is lower than or equal to the ISO rate, and the alternative hypothesis is that the AE rate for ZHR00 eyes is greater than the ISO rate. This criterion will be used for all ISO SPE rates, including secondary surgical interventions (SSI). In addition, rates for lens-related SSI due to optical issues causing visual symptoms will be presented with descriptive statistics.

$$H_0: p_t \leq p_i$$

$$H_1: p_t > p_i$$

where

$p_t$  = proportion of Model ZHR00 investigational lens eyes with the AE

$p_i$  = proportion of eyes reported in ISO SPE rates with the AE

Reject the null hypothesis if one-sided p-value < 0.025.

### CONTRAST SENSITIVITY

For contrast sensitivity data at 6 months postoperative, descriptive analyses including mean, standard deviation, median, minimum, maximum and two-sided 90% confidence intervals will be presented by IOL group for all levels of contrast and lighting conditions.

### VISUAL SYMPTOMS VIA PRO INSTRUMENT

For visual symptom data obtained from the PRVSQ instrument at 6 months postoperative, the frequency and proportion of subjects with a given response will be reported by IOL group.

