### QUESTIONNAIRES

Questionnaires will be administered at the 1-month and 6-month visits to collect information regarding spectacle usage, visual symptoms, visual quality and subject satisfaction. Four questionnaires will be used in this study:

- 1) Patient-Reported Visual Symptoms Questionnaire (PRVSQv2, **Appendix M**)
- 2) Patient-Reported Spectacle Independence Questionnaire (PRSIQv2, **Appendix N**)

- 3) Patient-Reported Spectacle Use Questionnaire (PRSUQ, **Appendix O**)
- 4) Patient-Reported Quality of Vision Questionnaire (Catquest-9SF, **Appendix P**)

In order to minimize any effect the doctor-patient relationship may have on a subject's responses on the questionnaire, the study questionnaires will be self-administered by the subjects. The questionnaires are to be administered at the start of the 1-month (second eye) and 6-month study visits, prior to any visual acuity testing.

In addition, if a subject is seen after the 1-month postoperative visit for an unscheduled visit due to an optical/visual symptom complaint, the PRVSQ will be administered at that visit, as well as prior to any secondary surgical intervention for an optical/visual symptom complaint. If additional unscheduled visits and/or a secondary surgical intervention due to the same optical/visual symptom complaint occur within 2 weeks of each other, it is not necessary to complete the PRO Visual Symptoms Questionnaire a second time.

The optical visual symptom complaints that trigger the PRO Visual Symptoms Questionnaire include any of the seven symptoms from the PRVSQ: halos, glare, starbursts, sensitivity to light, occlusions, double vision or poor light vision.

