## **10.8 EXIT OF SUBJECTS**

An Exit CRF will be completed for all subjects, either when they complete the study or if they exit early.

It is the responsibility of the investigator to provide complete follow-up data to JJSV for each subject, and every attempt should be made to gather that complete follow-up data for all subjects enrolled, as missing data can have a negative effect on the study results. Patients who would be traveling, relocating or otherwise unavailable for postoperative follow-up visits should not be enrolled in this clinical study.

A subject will be considered a "screen failure" if he/she does not meet the eligibility criteria or if consent is withdrawn prior to randomization.

A subject will be considered "discontinued prior to treatment" if the subject is randomized but does not undergo surgery or receive a study lens for various reasons including: the planned implant being aborted due to surgical complications, the subject withdrawing consent prior to treatment or the subject died prior to treatment.

Subjects will be "discontinued" from the study if one study lens (if implanted unilaterally) or both study lenses (if implanted bilaterally) are removed or if the subject dies.

If a subject receives at least one study lens, he/she is to be followed according to the schedule in Table 2 (Section 10.2) for visit windows.

Subjects will be considered “lost-to-follow-up” from the study only if irretrievably lost for unavoidable reasons such as: subject moved/unable to locate, subject ill/unable to travel, subject uncooperative/refuses further study participation. In the event of subject relocation, effort must be made by the investigator to secure follow-up information (i.e., slit-lamp findings and general visual acuity, etc.) from the subject’s new physician.

If a subject is exited early from the study, the investigator must indicate the reason for study exit on the CRF. In the event of a lens removal or other serious adverse event, the subject may be exited from the study; however, effort must be made by the investigator to follow the subject until resolution of the adverse event before exiting the subject from the study.

Following study completion or early exit, subjects will be informed about which lens model they received. Additionally, all study subjects are to be instructed to undergo regular eye examinations at least yearly and also to return to their doctor if any eye complications are experienced.

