The safety population will consist of all eyes and subjects implanted with either a test or control IOL(s) and with data available at the time of analysis (i.e., no data imputation). Reporting of cumulative complications and cumulative adverse event (occurring at any time postoperative either at standard visits or interim visits) will include data from all study eyes implanted. Thus, all adverse events at any postoperative visit (including standard or interim visit) will be reported unless it is results at a given visit (i.e., 6 months). For all safety endpoints, only the safety population will be used. For BCDVA, a best-case population will also be used, consisting of eyes in the safety population without any clinically-relevant preoperative ocular pathologies or macular degeneration detected at any time.

For the primary DCIVA, and secondary DCNVA, the mITT, PP and safety populations will be used for data reporting. For the defocus curve primary endpoint and overall spectacle independence secondary endpoint, only safety and PP populations will be used for data reporting. For safety endpoints and other endpoints, only the safety population will be used. The primary analysis will be based on first-eye data, unless stated otherwise. However, select data such as some visual acuity variables will also be reported separately for second eyes as supportive data only. Binocular data will be reported for those who are implanted with the same (test or control) IOL in both eyes. For demographics/enrollment/accountability data will also be reported for all randomized subjects whether an IOL was implanted or not with group assignment based on the randomization. Appendix I lists the analysis tables including the endpoints and the populations used to report the results.

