### 5.3.4 VISUAL SYMPTOMS VIA PRO INSTRUMENT

For the safety endpoint of visual symptoms via the Patient Reported Vision Symptoms Questionnaire (PRVSQ) at 6 months postoperative, the frequency and proportion of each response will be tabulated by IOL group.

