	First Eyes	First Eyes	Second Eyes	Second Eyes	Subjects	Subjects	Comments (population used for analysis)
	ZHR00	ZCB00	ZHR00	ZCB00	ZHR00	ZCB00	
Operative Data							
General Surgical Parameters: No. and Percent with each response	X	X	X	X			SF
Incision type (by type) Incision size in mm (<2.6, 2.6 to 2.7, 2.8 to 3.0, >3.0) Capsulorhexis diameter in mm (≤4.0, 4.1 to 5.0, >5.0) Capsulorhexis centration (centered/eccentric) Capsulotomy method (by type) Lens Removal Method (by method) Viscoelastic agent (by type) Implant instrument (by type) Lens placement (capsular bag, other) Type of closure (sutureless, suture)							
Surgical Complications: No. and percent with each response	X	X	X	X			SF
Surgical complications (none, all items listed on CRF, other) Other surgical procedures (none, all items listed on CRF, other)							
Lens Power Implanted (N, Mean, SD , Median, Min., Max. in Diopters (D))	X	X	X	X			SF

	First Eyes	First Eyes	Second Eyes	Second Eyes	Subjects	Subjects	Comments (population used for analysis)
	ZHR00	ZCB00	ZHR00	ZCB00	ZHR00	ZCB00	
PRIMARY EFFECTIVENESS ENDPOINTS							
Monocular DCIVA at 66cm (LogMAR) at 6M (N, Mean, SD, Median, Min., Max., 95% CI)	X	X	X	X			miITT/SF/PP/Sensitivity-1 st eyes (SF-2 nd as supportive data only)
Monocular defocus curve at 6M	X	X					SF/PP
SECONDARY EFFECTIVENESS ENDPOINTS							
Monocular DCNVA at 40cm (LogMAR) at 6M (N, Mean, SD, Median, Min., Max., 95% CI)	X	X	X	X			miITT/SF/PP/Sensitivity-1 st eyes (SF-2 nd as supportive data only)
Overall Spectacle independence at 6M (No. and percent of the response)					X	X	SF/PP bilateral subjects
SAFETY ENDPOINTS							
Monocular BCDVA (LogMAR) at 6M (N, Mean, SD, Median, Min., Max., 90% CI)	X	X	X	X			SF - 1 st eyes Sensitivity - 1 st eyes (SF-2 nd as supportive data only)
The number and percent of eyes with adverse events as described in ISO11979-7	X	X	X	X			SF - 1 st eyes (SF-2 nd as supportive data only)
Monocular contrast sensitivity at 6M (N, Mean, SD, Median, Min., Max., 90% CI)	X	X					SF
Ocular visual symptoms via questionnaire at 6M					X	X	SF
OTHER ENDPOINTS							
Visual Acuity – Intermediate							
Monocular DCIVA at 66cm (LogMAR) at 6M by Site (N, Mean, SD, Median, Min., Max.)	X	X					SF

	First Eyes	First Eyes	Second Eyes	Second Eyes	Subjects	Subjects	Comments (population used for analysis)

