Monocular defocus curve at 6M by photopic no glare pupil size ( $\leq 2.5$ mm, $>2.5$ to $<4$ mm and $\geq 4.0$ mm)	X	X					SF
Binocular defocus curve overall at 6M					X	X	SF Bilateral subjects
Binocular defocus curve at 6M by averaged photopic no glare pupil size ( $\leq 2.5$ mm, $>2.5$ to $<4$ mm and $\geq 4.0$ mm)					X	X	SF Bilateral subjects
Pupil Size							
Photopic Pupil Size at 6M (No. and percent $\leq 2.5$ mm, $>2.5$ to $<4.0$ mm and $\geq 4.0$ mm).	X	X	X	X			SF
Mesopic Pupil Size at 6M (No. and percent ( $\leq 4.0$ mm, $>4.0$ to $\leq 5.0$ mm, and $>5.0$ mm).	X	X	X	X			SF
Refractive Outcomes							
Refractive Outcomes (N, Mean, SD, Median, Min, Max, 95% CI)	X	X	X	X			SF

	First Eyes	First Eyes	Second Eyes	Second Eyes	Subjects	Subjects	Comments (population used for analysis)
	ZHR00	ZCB00	ZHR00	ZCB00	ZHR00	ZCB00	
Spherical Equivalent at 6M							
Adjusted Spherical Equivalent at 6M (Postop minus target)							
Absolute Refractive Cylinder at 6M							
Absolute Spherical Equivalent by Diopter Level (<=0.50, 0.51-1.00, 1.01-1.50, 1.51-2.00,>2.00) at 6M (No. and percent within each category)	X	X	X	X			SF
Absolute Refractive Cylinder by Diopter Level (<=0.50, 0.51-1.00, 1.01-1.50, 1.51-2.00,>2.00) at 6M (No. and percent within each category)	X	X	X	X			SF
Questionnaire Data							
No. and percent for all questionnaire responses at 1M and 6M					X	X	SF Bilateral subjects
Overall spectacle independence (second secondary effectiveness endpoint) by site (No and percent of the response) at 6M					X	X	SF Bilateral subjects
Other Contrast Sensitivity							
Monocular contrast sensitivity at 6M by pupil size (N, Mean, SD, Median, Min, Max, 90% C.I.)	X	X					SF
For mesopic lighting condition, by mesopic pupil category (<4.0 mm, >4.0 to ≤5.0 mm and >5.0 mm)							
For photopic condition, by photopic pupil size category ((≤2.5 mm, >2.5 to <4.0 mm and ≥4.0 mm							
Medical/Lens Findings and Other Adverse Event Tables							
Medical and Lens Findings at each visit and Cumulative (No. and percent with each item)	X	X	X	X			SF
Fundus finding at 6M (No. and percent Normal/Not Normal)	X	X	X	X			SF

	First Eyes	First Eyes	Second Eyes	Second Eyes	Subjects	Subjects	Comments (population used for analysis)
	ZHR00	ZCB00	ZHR00	ZCB00	ZHR00	ZCB00	
Fundus visualization at 6M (No. and percent adequate/not adequate)							
Listing of Adverse Events by site	X	X	X	X			SF

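### The 6-month visual-symptom table has no place for subjects whose lens was removed for symptoms, and the PRVSQ taken before removal is assigned to no table

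*Protocol*

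**What the plan says.** - **Endpoint.** Protocol 20.2 (Visual Symptoms via PRO Instrument) reads "For visual symptom data obtained from the PRVSQ instrument at 6 months postoperative, the frequency and proportion of subjects" with a given response, by lens group. SAP 5.3.4 matches it: "at 6 months postoperative, the frequency and proportion of each response will be tabulated by IOL group". The SAP Appendix I row under Safety Endpoints is "Ocular visual symptoms via questionnaire at 6M", in the safety population.
- **Missing data.** Protocol 20.1 and SAP 2.1 restrict the safety population to data on hand at the time of analysis and impute nothing.
- **Exit.** Under Protocol 10.8 a subject is discontinued "if one study lens (if implanted unilaterally) or both study lenses (if implanted bilaterally) are removed or if the subject dies". The same section allows, but does not require, exit after any lens removal.
- **Event-triggered forms.** Protocol 10.7 (Questionnaires) and 10.9 require the PRVSQ at an unscheduled visit for an optical or visual complaint after the 1-month visit, "as well as prior to any secondary surgical intervention for an optical/visual symptom complaint". A repeat within 2 weeks for the same complaint is waived.
- **Planned questionnaire tables.** SAP Appendix I lists "No. and percent for all questionnaire responses at 1M and 6M" and a separate 1-month visual-symptom row, both for bilateral subjects. No row covers unscheduled or pre-intervention forms.

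**The concern.** Protocol 17 expects halos, night glare and starbursts with ZHR00 and notes that the lens can be taken out if need be. Protocol 11.1 lists visual symptoms leading to secondary surgery, such as lens removal, among the anticipated serious adverse events. A subject who reaches that point is among those the symptom questionnaire most needs to describe, and is also the one most likely to have no 6-month form or one completed after the lens has gone. Absence from the table is then caused by the outcome that the table measures.

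The endpoint is a patient-reported safety comparison of a diffractive lens with a monofocal. It has no formal test, so readers will compare the tabulated proportions directly. If symptom-driven removals fall mostly in the ZHR00 arm, which is plausible but not stated, that comparison would favour ZHR00.

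The plan takes more care elsewhere. Mean BCDVA, also a safety endpoint, has worst-case and best-case sensitivity analyses. Spectacle independence has the percentage missing and the reasons reported. The PRVSQ endpoint has neither.

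**Working it through.** The documents give no expected symptom rate, removal rate, margin or power for this endpoint, so there is no plan figure to reproduce. The check has two parts.

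**Tracing a subject through the text**

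1. *Only study lens, or both study lenses, removed before 6 months.* Discontinued under Protocol 10.8. There is no 6-month PRVSQ and no imputation, so the subject is in neither numerator nor denominator.
2. *One of two lenses removed, subject exits.* Same result.
3. *One of two lenses removed, subject stays.* The PRVSQ (Protocol Appendix M) is completed per subject and asks about the last 7 days. Protocol Appendix Q defines removal as leaving a non-investigational lens or no lens. The 6-month answer therefore cannot describe that eye's symptoms before an earlier removal. Which group, if any, the subject belongs to in the 6-month table is not stated.
4. *Exchange or reposition.* Appendix Q defines exchange as replacement with the same model, and reposition leaves the existing lens in the eye. The 6-month answer still describes the study lens, so nothing is lost.

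In cases 1 to 3 the pre-intervention PRVSQ should exist under Protocol 10.7, but no analysis refers to it.

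**Size, with assumed counts**

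Let N be the subjects in one arm, r those removed for symptoms who gave the worst bother ratings beforehand, and k those giving such ratings at 6 months among the rest. Assume no other missing data.

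- As planned, removed subjects exit: k/(N − r)
- As planned, removed subjects stay, are counted, and no longer report it: k/N
- Pre-removal answers counted: (k + r)/N

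With N = 100, the evaluable number per group in Protocol 8:

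| k | r | Exit | Stay | Pre-removal counted |
|---|---|---|---|---|
| 5 | 0 | 5.00% | 5.00% | 5.00% |
| 5 | 1 | 5/99 = 5.05% | 5.00% | 6.00% |
| 5 | 2 | 5/98 = 5.10% | 5.00% | 7.00% |
| 5 | 5 | 5/95 = 5.26% | 5.00% | 10.00% |
| 2 | 2 | 2/98 = 2.04% | 2.00% | 4.00% |

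The shortfall is r/N if they stay. If they exit it is slightly less: for k = 5 and r = 2, 7.00 − 5.10 = 1.90 percentage points.

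With N = 112 (half of the 224 randomised in SAP 7.4) and r = 3:

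- k = 5: 5/109 = 4.6% (exact 95% CI 1.5 to 10.4) against 8/112 = 7.1% (3.1 to 13.6)
- k = 2: 2/109 = 1.8% against 5/112 = 4.5%

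**The case against.** The strongest reply is that nothing is decided by this table and that the affected subjects are not hidden. Both points are true. The endpoint is descriptive, with no hypothesis or success criterion. Lens-related secondary surgery for optical problems has its own descriptive rate (Protocol 20.2, SAP 5.3.2). Cumulative adverse events cover all implanted eyes, and listings give last reported status. Non-directed symptoms are asked at every postoperative visit, with severity for halos, night glare and starbursts, and are tabulated cumulatively. The 1-month PRVSQ table would include a bilateral subject whose lens was removed later. None of these supplies the PRVSQ frequency and bother ratings close to the removal, and none alters the 6-month proportions.

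A reader might also infer more than the documents support:

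- *That the pre-removal PRVSQ will never be analysed.* Protocol 6 says data from other visits enter the final analysis, and Protocol 20 says other time points will be reviewed. These statements are general and name no PRVSQ output. The supportable claim is that no table is specified.
- *That a subject with one lens replaced is counted under the implanted lens and dilutes that group.* No passage says so. Protocol 20.3 and SAP 6.6 limit satisfaction and other questionnaire results to subjects who received the same lens in both eyes, while the 6-month symptom row says only safety population. The handling is open, so dilution is possible but not established.
- *That the earlier form should replace the 6-month one after any symptom-driven surgery.* After a same-model exchange or a reposition, that would discard valid answers about the study lens.

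**Conclusion.** The gap is real and worth closing, as a matter of reporting rather than inference. As written, the 6-month PRVSQ table omits subjects discontinued after symptom-driven removal, leaves unstated how it treats those with one lens removed, and makes no use of forms collected for this situation. It can understate severe symptoms.

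By how much is unknown. The percentages above rest wholly on assumed r and k, on every removed subject having given the worst ratings beforehand, and on no other missing data, although the plan allows for about 10% drop-out. Under those assumptions, with 100 subjects, each removal costs about one percentage point. That is small in absolute terms but large relative to a rare category. With no removals there is no difference. The wide intervals also show that a few subjects would not settle a comparison. No control-arm removal figures exist, so bias between the arms is a plausible direction drawn from Protocol 17, not a demonstrated effect. No test, sample size or success criterion changes.

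**What to change.** Amend SAP 5.3.4 and Appendix I before database lock:

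1. Keep the planned 6-month table, and state how a subject with one of two study lenses removed is handled in it.
2. Add a table by lens group that keeps every subject with a study lens removed for an optical or visual complaint in the implanted group's denominator. Use the last PRVSQ before removal, or show these subjects in a separate category for lens removed for visual symptoms. The separate category also covers any subject with no form before removal, and avoids carrying an earlier value into a no-imputation population.
3. Add a table or listing, by lens group, of all unscheduled and pre-intervention PRVSQ forms. Label it as event-triggered, since subjects who complain complete more forms.

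Leave the 6-month form in place after a reposition or same-model exchange.

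The cost is SAP wording and one or two outputs from data that the protocol already requires. Assessment times will be mixed for a few subjects in the added table, and ZHR00 symptom rates may look slightly worse.
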